5.4.2.2 Diagnostic performance of ¹⁸F-fluciclovine

Diagnostic performance will be assessed by calculating sensitivity, specificity, Positive Predictive Value (PPV), and Negative Predictive Value (NPV), using subject based analyses. Further calculations will be made for intra-prostatic / prostate bed and extra-prostatic disease. Reference tests will be the adjudication panel decision. The Adjudication Panel will follow the Adjudication Manual that prospectively documents the processes to be used to determine a decision concerning the result of the ¹⁸F-fluciclovine PET/CT scan vs standard of truth. The number and percentage of indeterminate responses will be reported.

The sensitivity, specificity, PPV and NPV will be calculated as:

- Sensitivity = $TP / (TP + FN)$
- Specificity = $TN / (FP + TN)$
- PPV = $TP / (TP + FP)$
- NPV = $TN / (FN + TN)$

where TP, TN, FP and FN refer to true positive, true negative, false positive and false negative results respectively.

Definitions of these summaries will be based on the table below.

		Reference tests		
		Positive	Negative	
Fluciclovine (¹⁸ F) scan results	Positive	True Positive (TP)	False Positive (FP)	TP+FP
	Negative	False Negative (FN)	True Negative (TN)	FN+TN
		TP+FN	FP+TN	n

The number, percentage and exact 95% CIs of TP, FP, FN and TN, as well as the point estimates (expressed in percentages) and their associated exact 95% CIs, of the Sensitivity, Specificity, PPV and NPV, will be presented at the subject level and the region level for the FAS, where the region level estimates will be calculated separately for each region: prostatic region and extra-prostatic region. The region level results will be derived at the subject level for each region resulting in one outcome for each subject in each region. For the subject level analysis, if a subject has at least one positive result, the subject will be categorised as positive. If all of a subject's results are negative the subject will be categorised as negative. For the region level analysis, if a subject has at least one positive result from the prostatic region the subject will be categorised as positive for the prostatic region. If all results related to the prostatic region are negative for a subject, that subject will be categorised as negative for the prostatic region. Similar classification rules apply for the extra-prostatic region.

Note that the subgroup analyses will only be performed if there are sufficient data for these analyses to be meaningful.

These estimates will be repeated separately for regionally recurrent disease (prostate/prostate bed), pelvic lymph nodes and distant metastases (retroperitoneal lymph nodes, other lymph nodes, soft tissue/parenchyma and bones), a summary for lymph nodes (overall) will also be presented. Once again the region level results will be derived at the subject level and subjects will be categorised as positive or negative for each region in a similar manner to that described above for the prostatic region.

These subject and location level summaries will be repeated by the following baseline PSA subgroups:

- 0 – 0.2
- >0.2 – 0.5
- >0.5 – 1.0
- >1.0 – 2.0
- 2.0 – 5.0
- 5.0 – 10.0
- >10.0

and across the following baseline Gleason score categories: ≤ 6 , 7, 8 and ≥ 9 . All these summarise will be repeated for the PPS.

All ^{18}F -fluciclovine PET/CT results, other imaging results and adjudication decision data will be listed.

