	
 2. The rate of detection of any disease site by ¹⁸F-fluciclovine PET/CT in the study population. 3. The rate of detection of 1) prostatic bed and other pelvic disease and 2) distant metastases (i.e., bone metastases, visceral metastases, or non-regional nodal metastases) with ¹⁸F-fluciclovine PET/CT in the study population. 4. The PPV of ¹⁸F-fluciclovine PET/CT to detect regionally recurrent disease compared to biopsy in those patients who undergo a regional disease biopsy on the basis of a ¹⁸F-fluciclovine PET/CT finding or in case of bony disease a correlation with MRI or biopsy. 5. The PPV of ¹⁸F-fluciclovine PET/CT to detect distant disease compared to biopsy in those patients who undergo a distant disease biopsy on the basis of a ¹⁸F-fluciclovine PET/CT finding or in case of bony disease a correlation with MRI or biopsy. 
An independent adjudication panel will review and adjudicate ¹⁸F-fluciclovine PET/CT lesions with biopsy or MRI during follow-up to assess the PPV and, where possible, NPV, sensitivity and specificity. Rates of disease detection (radiographic only and confirmed by pathology or MRI) will be described

Safety Evaluations	Monitoring for adverse events, change in EKGs and routine hematology and biochemistry evaluations taken prior to and following receipt of ¹⁸ F-fluciclovine
Planned Interim Analyses	An interim analysis of a subset of study results on all enrolled subjects may be submitted for potential public presentation prior to completion of all data collection and analyses. As trial design will not be modified as a result of this interim analysis, no adjustment to the type I error is required.
STATISTICS Primary Analysis Plan	For the evaluation of the primary endpoint (i.e., impact on therapy), questionnaires obtained pre- and post- ¹⁸ F-fluciclovine PET/CT will be compared to calculate the fraction of cases with a change in management (versus no change in planned management). The 95% confidence interval will be calculated using the Exact method for a binomial distribution.

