Actual Management Plan. At the final follow up visit any deviations or changes to the Revised Management Plan will be documented

9. Biopsy

Biopsy is not required by the protocol; however patients with PET/CT positive findings in soft-tissue supported by anatomical abnormalities on CT or MRI may have a biopsy performed per standard practice where the procedure is deemed clinically feasible and safe. Biopsies completed within 4 months after imaging will contribute to the aim of the study.

1. Biopsy results of suspected bone metastases conducted per standard practice will also be collected. Bone lesions may be followed up through imaging where biopsy is not practical.
2. Based on local-radiologist/nuclear medicine physicians assessment of ¹⁸F-fluciclovine PET/CT-positive findings supported by anatomic abnormalities, conduct imaging-guided biopsy of soft-tissue ¹⁸F-fluciclovine -enhancement region per institutional standard of care;
3. Submit pathology report(s) to the ACR Core Laboratory. The address is given in the Imaging Manual.

10. Blood Chemistry Profile

Blood will be obtained and sent to each site's clinical chemistry lab for determination of serum sodium, potassium, calcium, chloride, BUN, creatinine, glutamic oxaloacetic transaminase (SGOT/AST), glutamic-pyruvic transaminase (SGPT/ALT), alkaline phosphatase, creatine kinase (CK), lactate dehydrogenase (LDH), albumin, total protein, total bilirubin.

11. Hematology

Blood will be obtained and sent to each site's clinical hematology lab for a complete blood count (hemoglobin, hematocrit, red blood cell count, white blood cell count, white blood cell differential, and platelet count determinations).

12. Urinalysis

Prior to the ¹⁸F-fluciclovine dosing a midstream sample of urine will be obtained and tested by dipstick for leukocytes, nitrite, pH, protein, ketones, glucose, bilirubin, urobilinogen, and blood. This will not be repeated following scanning unless clinically indicated.

13. Adverse Events

See Section 12.

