14.2 Analysis of Secondary Endpoints

For the evaluation of the secondary endpoint examining actual impact on therapy, questionnaires obtained pre-FACBC will be compared to treatment executed post-¹⁸F-fluciclovine PET/CT to calculate the fraction of cases with a change in management (versus no change in planned management). For the estimation of detection rate, the proportion of the ¹⁸F-fluciclovine -PET/CT positive results, 95% confidence interval will be calculated using the Exact method for a binomial distribution.

For each patient a comparison will be made of the results of the ¹⁸F-fluciclovine PET/CT results, any histopathology results, results of any other imaging and also for the clinical response to treatment(s) (standard of truth) by an Adjudication Panel. The PPV, NPV, sensitivity and specificity will be calculated, where possible, at lesion or regional or patient level. The PPV will be calculated separately for patients undergoing optional biopsy for (1) regional disease and (2) distant disease. The 95% confidence interval will be calculated using the Exact method for a binomial distribution. The Adjudication Panel will follow the Adjudication Manual that will prospectively document the processes to be used to determine a decision concerning the result of the ¹⁸F-fluciclovine PET/CT scan vs standard of truth.

Rates of disease detection (radiographic only and confirmed by pathology or MRI) will be described

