3.5 Changes from the Protocol Planned Analysis

PPV efficacy variable (section 5.2) will be determined using adjudication panel decision rather than only using biopsy or biopsy/MRI data. This is consistent with the study objectives.

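### Sensitivity and specificity have no rule for indeterminate panel decisions and no allowance for scan-dependent verification, so they may be biased with exact CIs that do not show it

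*SAP*

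**What the plan says.** SAP 5.4.2.2 sets out the accuracy analysis: "Diagnostic performance will be assessed by calculating sensitivity, specificity, Positive Predictive Value (PPV), and Negative Predictive Value (NPV), using subject based analyses". The reference is a panel: "Reference tests will be the adjudication panel decision". The four measures are ratios of TP, FP, FN and TN from a table whose reference has two columns, positive and negative. They are presented with exact 95% intervals for the FAS, by subject and by region. On subjects the panel cannot classify, the section says only: "The number and percentage of indeterminate responses will be reported". SAP sections 2 and 5.4.3 rule out imputation.

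Three places bear on who is likely to receive a determinate decision:

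- Protocol 9.2, item 9: "Biopsy is not required by the protocol; however patients with PET/CT positive findings in soft-tissue supported by anatomical abnormalities on CT or MRI" may have one under standard practice.
- The Protocol Synopsis has the panel adjudicate PET/CT "lesions with biopsy or MRI during follow-up to assess the PPV and, where possible, NPV, sensitivity and specificity".
- Protocol 14.2 is broader. For each patient the panel considers the scan, any histopathology, and "results of any other imaging and also for the clinical response to treatment(s) (standard of truth) by an Adjudication Panel".

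SAP 3.5 records one change, for PPV: it "will be determined using adjudication panel decision rather than only using biopsy or biopsy/MRI data". Both the Synopsis and Protocol 14.2 limit sensitivity, specificity and NPV to what is possible. SAP 5.4.2.2 keeps a data-sufficiency condition only for subgroup analyses.

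**The concern.** Sensitivity and specificity are proportions among the diseased and the disease-free. If the chance of a determinate decision differs by scan result, the determinate subjects are not a fair sample of either group, and the raw ratios are off even in a large trial. This is partial verification bias. A Clopper-Pearson interval covers sampling error only, so it can be narrow around the wrong value.

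The setting invites such a difference. All subjects enter on PSA evidence of recurrence with negative or equivocal conventional imaging, so true absence of disease after a negative scan is hard to establish. A positive finding gives a target for biopsy or MRI. The question recurs in each region, since a scan-negative region offers little to biopsy. At stake is whether the reported sensitivity and specificity can be read as properties of the scan.

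**Working it through.** **The plan's own figures.** The documents give no target, sample size or precision for sensitivity or specificity, so there is nothing to reproduce for these measures. Two inputs come from Protocol 14.4: 40% scan-positive and 292 enrolled. The latter reproduces as 248/0.85 = 291.8, rounded up to 292.

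**Other inputs.** Three pairs of true values are used:

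- A: Se 0.55, Sp 0.95, the lower ends of the ranges in Protocol 1.1 for disease outside the prostate bed.
- B: Se 0.75, Sp 0.80, assumed middle values.
- C: Se 0.90, Sp 0.67, from Protocol 1.1 for the prostate bed, at the upper end of its specificity range.

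The determinacy rates after a positive scan (v+) and a negative scan (v−) are assumptions.

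**Formulas.** If indeterminate subjects drop out and determinacy depends on the scan result alone:

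- apparent Se = Se·v+ / [Se·v+ + (1−Se)·v−]
- apparent Sp = Sp·v− / [Sp·v− + (1−Sp)·v+]

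For A at 70%/35%: Se = 0.385/(0.385 + 0.1575) = 0.710; Sp = 0.3325/(0.3325 + 0.035) = 0.905.

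| True Se / Sp | v+ = v− | 70% / 35% | 80% / 20% |
|---|---|---|---|
| A: 0.55 / 0.95 | 0.55 / 0.95 | 0.710 / 0.905 | 0.830 / 0.826 |
| B: 0.75 / 0.80 | 0.75 / 0.80 | 0.857 / 0.667 | 0.923 / 0.500 |
| C: 0.90 / 0.67 | 0.90 / 0.67 | 0.947 / 0.504 | 0.973 / 0.337 |

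**Coverage of the nominal 95% exact intervals**, from 4,000 simulated trials of 292 scanned subjects, 40% positive:

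| Case | v+ / v− | Se | Sp |
|---|---|---|---|
| A | 70% / 35% | 8% | 86% |
| A | 80% / 20% | 0% | 60% |
| B | 70% / 35% | 50% | 27% |
| B | 80% / 20% | 3% | 0.1% |

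At 50%/50%, coverage was at least 95% in both cases. PPV and NPV intervals kept at least 95% in every scenario: within one scan result, the common rate v+ or v− cancels from the ratio.

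**What a correction and bounds would show.** Take case A per 1,000 scanned. A positive rate of 40% implies prevalence (0.40 − 0.05)/(0.55 − 0.05) = 0.70, hence TP 385, FP 15, FN 315, TN 285. At 70%/35% the determinate cells are 269.5, 10.5, 110.25 and 99.75, leaving 120 positives and 390 negatives indeterminate.

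- Begg-Greenes rescales within scan result: TP = 400 × 269.5/280 = 385; FN = 600 × 110.25/210 = 315; Se = 385/700 = 0.55. Likewise TN = 285 and FP = 15, so Sp = 0.95.
- Bounds for Se: 269.5/(269.5 + 110.25 + 390) = 0.350 to 389.5/(389.5 + 110.25) = 0.779.
- Bounds for Sp: 99.75/(99.75 + 10.5 + 120) = 0.433 to 489.75/(489.75 + 10.5) = 0.979.

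**Other mechanisms.** The direction changes if determinacy works differently. For case A:

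- Unverified negatives counted as TN at 80%/20%: Sp 0.978, so too high.
- v+ = 50%, with negatives determinate in 60% if diseased and 10% if not: Se 0.505, so too low.
- v+ = 50%, with 10% if diseased and 60% if not: Se 0.859 and Sp 0.958, both too high.

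**The case against.** The strongest reply is that biopsy is not the reference standard. Protocol 14.2 gives the panel other imaging and clinical response for each patient, and Protocol 10.6 abstracts PSA, biopsy and restaging results over six months. A scan-negative man can therefore be determinate without a biopsy, and the gap between v+ and v− may be smaller than the biopsy text suggests. This stands, and it limits the size of the problem. It does not show that determinacy is equal by scan result, and the Synopsis wording points the other way.

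A second reply is that the SAP never says indeterminate subjects are excluded. It names the FAS, and SAP 5.4.2.3 uses n from the same table for detection rates in all FAS and PPS subjects. This also stands: exclusion is the likeliest reading of a two-column table without imputation, but it is not a stated rule. For the same reason, a reader who infers that the detection rate is inflated as well goes beyond the text.

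A reader might also infer that sensitivity will be inflated and specificity deflated. The documents do not support that certainty. The direction depends on how indeterminates are classified and why scan-negative subjects become determinate. Those rules belong to the Adjudication Manual, which is not among the documents.

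Finally, Begg-Greenes carries its own assumption. If PSA course or treatment response makes determinacy depend on disease status given the scan, it is biased too. So it should not replace the raw estimates.

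**Conclusion.** The gap is real but its effect is conditional. The plan has no stated place for indeterminate decisions in the accuracy table, does not report determinacy by scan result, and plans no bounds or corrected analysis. If indeterminate subjects drop out and scan-positives are determinate more often, sensitivity is most plausibly too high and specificity too low, and the exact intervals do not reflect it.

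The size cannot be fixed from the documents. For case A it runs from no bias at equal rates to an apparent 0.83 for both measures at 80%/20%. More extreme figures follow from assuming that very few scan-negatives are determinate, for which the documents give no basis.

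The reach is limited. The primary endpoint does not use the panel. PPV, the only one of the four measures listed in SAP 5.2, is not distorted if determinacy depends on the scan result alone, and nor is NPV. Withholding NPV on this ground is therefore not justified. This is an inexpensive improvement to supportive measures, not a flaw in the main result.

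**What to change.** In SAP 5.4.2.2, before database lock:

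1. Report determinate and indeterminate counts by scan result, overall and per region.
2. Keep the raw sensitivity and specificity, labelled as based on determinate subjects.
3. Add best- and worst-case bounds that assign indeterminate subjects as diseased or disease-free.
4. Add a Begg-Greenes estimate with a suitable interval, for example bootstrap, as a sensitivity analysis. State its assumption that determinacy depends only on the scan result.
5. Restore the protocol's where-possible limit for sensitivity and specificity, so that they are not interpreted when few scan-negative subjects are determinate.

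No new data are needed. The cost is extra programming and wider intervals; the bounds in particular may be wide, as in the example above.

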3.2 Secondary Objectives

1. To measure the fraction of patients for whom ^{18}F -fluciclovine PET/CT leads to a change of actual management by comparison with the intended management plan before ^{18}F -fluciclovine PET/CT.
2. To estimate the fraction of patients in whom ^{18}F -fluciclovine PET/CT yields evidence of recurrent disease on the basis of imaging results.
3. To estimate 1) the rates of detecting regionally recurrent disease (i.e., prostatic bed-only and/or pelvic disease outside of the bed) and 2) the rate of detecting distant metastases (i.e., bone metastases, visceral metastases, or non-regional nodal metastases) with ^{18}F -fluciclovine PET/CT in the study population.
4. To determine 1) the PPV of ^{18}F -fluciclovine PET/CT to detect regionally recurrent disease and 2) the PPV of ^{18}F -fluciclovine PET/CT to detect distant metastases in the study population in patients who undergo optional biopsy of ^{18}F -fluciclovine PET/CT findings or have documentation of disease status based on other imaging and/or follow-up data. For soft tissue disease these calculations will be limited to those patients who undergo a confirmatory biopsy and for bone disease those with confirmatory findings on MRI any time during the 6-month follow up. The denominator for the analysis will be [lesions biopsied + bone lesions].
5. To explore differences in estimated cost of treatment plans determined prior to and following ^{18}F -fluciclovine PET/CT.

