3 STUDY OBJECTIVES AND DESIGN

3.1 Study Objectives

The primary objective of the study is to measure the fraction of subjects for whom ¹⁸F-fluciclovine PET/CT alters intended management through detection of disease after curative-intent treatment in a population of men with elevated prostatic specific antigen (PSA) levels indicative of persistent or recurrent prostate cancer and negative or equivocal findings on standard-of-care diagnostic imaging tests.

The secondary objectives of the study are

- To measure the fraction of subjects for whom ¹⁸F-fluciclovine PET/CT leads to a change in actual management by comparison with the intended management plan before ¹⁸F-fluciclovine PET/CT
- To estimate the fraction of subjects in whom ¹⁸F-fluciclovine PET/CT yields evidence of recurrent disease on the basis of imaging results
- To estimate:

- the rates of detecting regionally recurrent disease (i.e. prostatic bed-only and/or pelvic disease outside of the bed)
 - the rate of detecting distant metastases (i.e. bone metastases, visceral metastases, or non-regional nodal metastases)
- with ^{18}F -fluciclovine PET/CT in the study population
- To determine:
 - the positive predictive value (PPV) of ^{18}F -fluciclovine PET/CT to detect regionally recurrent disease
 - the PPV of ^{18}F -fluciclovine PET/CT to detect distant metastases in the study population in subjects who undergo optional biopsy of ^{18}F -fluciclovine PET/CT findings or have documentation of disease status based on other imaging and/or follow-up data
 - To explore differences in estimated cost of treatment plans determined prior to and following ^{18}F -fluciclovine PET/CT

[figure not shown]

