5.2 Secondary Efficacy Variables

The secondary efficacy variables are:

- Per subject impact (yes/no) of ^{18}F -fluciclovine PET/CT on pre-PET intended versus post-PET actual subject management
- The rate of detection of any disease site by ^{18}F -fluciclovine PET/CT in the study population
- The rate of detection of:
 - Prostatic bed and other pelvic disease
 - Distant metastases (i.e. bone metastases, visceral metastases or non-regional nodal metastases)with ^{18}F -fluciclovine PET/CT in the study population
- The PPV of ^{18}F -fluciclovine PET/CT to detect regionally recurrent disease compared to adjudication panel decision.
- The PPV of ^{18}F -fluciclovine PET/CT to detect distant metastases compared to adjudication panel decision.

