5.3 Definition of Region Levels

Two main regions will be analysed, the prostate and prostate bed and the extra-prostatic region.

The prostate and prostate bed include the following lesion locations:

- Prostate bed left
- Prostate bed right

- Peripheral zone left
- Peripheral zone right
- Central gland left
- Central gland right
- Left seminal vesicle
- Right seminal vesicle

The extra-prostatic regions include the following lesion locations

- Lymph nodes
 - Pelvic lymph nodes
 - Common iliac left
 - Common iliac right
 - Internal iliac left
 - Internal iliac right
 - External iliac left
 - External iliac right
 - Obturator left
 - Obturator right
 - Pre-sacral left
 - Pre-sacral right
 - Peri-rectal anterior
 - Peri-rectal posterior
 - Inguinal left
 - Inguinal right
 - Retroperitoneal lymph nodes
 - Para-aortic
 - Retro-aortic
 - Para-caval
 - Retro-caval
 - Aorto-caval
 - Retrocrural left
 - Retrocrural right
 - Other lymph nodes
 - Intra-peritoneal
 - Mediastinal left
 - Mediastinal right
 - Axillary left
 - Axillary right
 - Cervical left
 - Cervical right
- Soft tissues/parenchyma
 - Lung upper lobe left
 - Lung upper lobe right
 - Lung middle lobe left
 - Lung middle lobe right
 - Lung lower lobe left
 - Lung lower lobe right

- Brain left
- Brain right
- Liver left
- Liver right
- Spleen
- Subcutaneous/cutaneous
- Muscle
- Bowel
- Bones
 - Skull
 - Skull base/maxilla left
 - Skull base/maxilla right
 - Mandible left
 - Mandible right
 - Neck
 - Vertebra C1
 - Vertebra C2
 - Vertebra C3
 - Vertebra C4
 - Vertebra C5
 - Vertebra C6
 - Vertebra C7
 - Vertebra T1
 - Vertebra T2
 - Vertebra T3
 - Vertebra T4
 - Vertebra T5
 - Vertebra T6
 - Vertebra T7
 - Vertebra T8
 - Vertebra T9
 - Vertebra T10
 - Vertebra T11
 - Vertebra T12
 - Vertebra L1
 - Vertebra L2
 - Vertebra L3
 - Vertebra L4
 - Vertebra L5
 - Sacrum left
 - Sacrum right
 - Sacrum central
 - Chest
 - 1st rib left
 - 1st rib right
 - 2nd rib left
 - 2nd rib right
 - 3rd rib left
 - 3rd rib right
 - 4th rib left
 - 4th rib right
 - 5th rib left
 - 5th rib right

- 6th rib left
- 6th rib right
- 7th rib left
- 7th rib right
- 8th rib left
- 8th rib right
- 9th rib left
- 9th rib right
- 10th rib left
- 10th rib right
- 11th rib left
- 11th rib right
- 12th rib left
- 12th rib right
- Sternum
- Clavicle left
- Clavicle right
- Scapula left
- Scapula right
- Pelvis
 - Ilium left
 - Ilium right
 - Superior pubic ramus left
 - Superior pubic ramus right
 - Inferior pubic ramus left

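### The SAP calculates the PPV for regionally recurrent disease on the prostate/prostate bed alone, although the objectives define it as bed and/or other pelvic disease, and it does not declare the narrowing

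*SAP*

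**What the plan says.** The third secondary objective in Protocol 3.2 gives the definition: "regionally recurrent disease (i.e., prostatic bed-only and/or pelvic disease outside of the bed". SAP 3.1 repeats it: "the rates of detecting regionally recurrent disease (i.e. prostatic bed-only and/or pelvic disease outside of the bed". In both documents the next objective, on PPV, reuses the term and offers no other meaning.

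Both documents then name two PPVs. Protocol 14.2: "The PPV will be calculated separately for patients undergoing optional biopsy for (1) regional disease and (2) distant disease". SAP 5.2 lists one PPV "to detect regionally recurrent disease compared to adjudication panel decision" and one "to detect distant metastases compared to adjudication panel decision".

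On regions, SAP 5.3 says "Two main regions will be analysed, the prostate and prostate bed and the extra-prostatic region", and places the pelvic lymph nodes under the extra-prostatic heading. SAP 5.4.2.2 follows this ("the region level estimates will be calculated separately for each region: prostatic region and extra-prostatic region") and then adds further groupings: "These estimates will be repeated separately for regionally recurrent disease (prostate/prostate bed), pelvic lymph nodes and distant metastases". Its distant group consists of retroperitoneal nodes, other nodes, soft tissue/parenchyma and bone. It also adds a summary for all lymph nodes.

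SAP 3.5, on changes from the protocol analysis, declares one change to the PPV: the adjudication panel replaces biopsy or biopsy/MRI as the reference.

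**The concern.** The row carrying the secondary endpoint's name covers less than its objective. Read literally, the regional PPV reported from this trial would be a bed-only PPV, and a reader of the objectives would take it to include pelvic nodes.

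The choice could matter. Protocol 1.1 quotes specificity of 40-67% in the prostate bed and more than 95% outside it, so the bed PPV and the pelvic-node PPV need not agree. A combined figure added after the results are known would be post hoc, although it is the estimate the objective asks for.

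**Working it through.** The plan gives no figure to reproduce here, so the check compares definitions with planned output and then tests whether the missing estimate could be rebuilt.

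**1. What each PPV grouping in SAP 5.4.2.2 contains**

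| Grouping | Bed | Pelvic nodes | Distant sites |
|---|---|---|---|
| Subject level | yes | yes | yes |
| Prostatic region | yes | no | no |
| Extra-prostatic region | no | yes | yes |
| Row labelled regionally recurrent disease | yes | no | no |
| Pelvic lymph nodes | no | yes | no |
| Distant metastases | no | no | yes |
| Lymph nodes overall | no | yes | nodes only |
| *Needed by the objective* | *yes* | *yes* | *no* |

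No planned row has the pattern of the last line. A subject positive only in pelvic nodes is counted at subject level and in the extra-prostatic, pelvic-node and all-node rows, but in neither PPV that SAP 5.2 names.

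**2. Can the combined PPV be rebuilt from the bed and pelvic-node rows?**

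The documents give no counts, so these are assumed:

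- Bed: 80 scan-positive, 60 true and 20 false (60/80 = 75%).
- Pelvic nodes: 20 scan-positive, 18 true and 2 false (18/20 = 90%).

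For scale, Protocol 14.4 assumes 40% positivity and 15% data loss with 292 to 330 enrolled. That gives 0.40 × 0.85 × 292 = 99.3 to 0.40 × 0.85 × 330 = 112.2 positive subjects. The assumed total is of that order, but it leaves little room for subjects positive only at distant sites.

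Count a subject as a combined true positive if true positive in at least one of the two places (an assumption). Let *k* be the subjects positive in both places and *t* those true positive in both. Then

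combined PPV = (60 + 18 − t) / (80 + 20 − k) = (78 − t) / (100 − k).

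- No overlap (k = 0, t = 0): 78/100 = 78.0%.
- Lowest (k = 18, t = 18): 60/82 = 73.2%.
- Highest (k = 20, t = 0): 78/80 = 97.5%.

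The same two published rows therefore fit a combined PPV below or above the bed-only 75%, depending on an overlap that the rows do not show.

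A second assumed pair leads to the same conclusion. With bed 28/40 (70%), nodes 27/30 (90%) and 20 subjects positive in both, the combined PPV runs from 35/50 = 70% to 50/50 = 100%.

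**The case against.** The definition is written in the detection-rate objective and reaches the PPV only because the term is reused. That objective could also be read as asking for bed and pelvis separately, since it speaks of rates in the plural. This reading does not survive the endpoint text: Protocol 5.2 and SAP 5.2 treat bed and other pelvic disease as one item, set against distant metastases. No narrower meaning of regional appears before SAP 5.4.2.2.

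SAP 5.4.2.3 also splits the detection rate into bed, other pelvic disease and distant metastases without a combined figure. That is true, but it does not put the name of the regional endpoint on the bed row.

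Several points do stand:

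- Pelvic nodes are analysed, in their own row with an exact CI.
- The differing specificities are a good reason to show bed and nodes separately, and those rows should stay.
- The endpoint is secondary and descriptive. Scan and adjudication results are listed, so the combined PPV could be derived later.
- The table shells and the Adjudication Manual are separate documents that were not available. Either might define the grouping, but the label in the SAP text would still conflict with the objectives.
- The numerical range rests on assumed counts, and its upper end needs an extreme overlap: 18 of the 20 bed false positives would have to be node true positives. The calculation also ignores missed disease. If the reference too is called positive on any positive site, a bed false positive with a missed pelvic node becomes a combined true positive. That would widen the range, so the conclusion that the figure cannot be recovered is not weakened.

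**Conclusion.** The concern holds. As written, SAP 5.4.2.2 attaches the name of a secondary endpoint to a narrower region than its objective defines, provides no row for the defined region, and does not declare the change. It should be corrected before database lock.

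How far, and in which direction, the reported regional PPV would differ from the intended one cannot be established from the documents. The 73.2% to 97.5% range shows only that the bed and node rows do not determine the combined value. The conclusion rests on carrying the definition from the detection-rate objective into the PPV objective, and it is limited to the SAP text.

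**What to change.** Before database lock:

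- In SAP 5.3, define a composite region of prostate/prostate bed plus pelvic lymph nodes, with one outcome per subject. Pelvic nodes are the only pelvic sites outside the bed that SAP 5.4.2.2 does not assign to distant metastases, so this composite matches the objective. The text should state that equivalence.
- In SAP 5.4.2.2, report the composite's PPV with an exact 95% CI as the regional secondary endpoint. Keep the bed and pelvic-node rows and relabel them as components.
- If a bed-only PPV is what is wanted, declare and justify it in SAP 3.5 instead.
- A matching combined detection rate in SAP 5.4.2.3 is optional.

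The cost is some SAP wording and one added row per PPV table. The node locations are already listed in SAP 5.3, and the subject-level data are already collected.
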